8.3.2.16 Change in Hospital Anxiety and Depression Scale (HADS) score

The HADS observed scores and changes from Baseline for depression and anxiety will be listed by subject.

8.3.2.17 Change from baseline in seizure frequency

The 28-day adjusted seizure frequency and change from baseline will be summarized descriptively by the treatment group in Titration and Stabilization, Maintenance, and Treatment Periods for observable focal-onset seizures and Type I seizures. The imputation rule described in Section 4.2.1 will be applied.

8.3.2.18 Use of health-related outcomes and HRU

Health-related outcomes data and HRU data will be listed for the RS.

- Socio-professional status

Socio-professional status data are collected at Visit 1 and Visit 7/EDV. Variables include highest level of education, housing status, current professional status, current unemployed status, need for regular assistance due to epilepsy, and ability to drive..

- Healthcare provider consultations not foreseen by the protocol

The health care provider consultations by type of provider (general practitioner, specialist physician, nurse, and other) per subject will be listed.

- Hospital and ER visits

ER visits will be extracted from the Hospitalization/ER Visit CRF page (if the initial entry point is ER).

- Caregiver assistance

Caregiver assistance data is collected on the CRFs “Caregiver Assistance Screening” and “Caregiver Assistance Follow-up”. Data will be listed per visit.

- Number of school or working days lost

Number of school/working days lost data are collected on the CRFs “School and Workdays Lost Screening” and “School and Workdays Lost Follow-up”. The number and percentages of subjects who lose school or work days as a result of epilepsy will be listed.

The percentage of days lost will be listed by visit for subjects who have more than zero total number of school or work days. The percentage of days lost will be calculated as:

$100 \times (\text{end date of absence} - \text{start date of absence} + 1) / (3 \times 30 + 1)$ for the screening visit. If the end date of absence is missing or after Visit 1 date, the end date of absence will be set to Visit 1; if the start date of absence is missing or prior to Visit 1-90, the start date of absence will be set to Visit 1-90.

$100 \times (\text{end date of absence} - \text{start date of absence} + 1) / (\text{visit date of current visit} - \text{visit date of previous visit} + 1)$ for the later visits. If the end date of absence is missing or after the current visit date, the end date of absence will be set to the current visit date; if the start date of absence is missing or prior to the previous visit+1, the start date of absence will be set to the previous visit date+1.

If multiple absences are reported at a given visit, the sum of the duration of all absences will be used in the numerator.

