#### **9.5 Health-related outcomes and healthcare resource utilization**

Health-related outcomes and HRU will be collected in the eCRF and/or diary during the study according to the tabular schedule of assessments (Table 5-1).

These assessments will include:

- Socio-professional status
- Healthcare provider consultations not foreseen by the protocol including the type of provider (general practitioner, specialist physician, nurse), the site of care (office-private, office-hospital, home, emergency room), and the reason leading to the consultation
- Concurrent medical procedures
- Concomitant medications
- Hospitalizations including the reason leading to the hospitalization, admission ward transfers, and length of stay
- Caregiver support needs
- Number of school or working days lost due to the medical condition of the subjects

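### After screening, the percentage of school or work days lost is divided by one day more than can be counted, and it is a calendar-day figure that is not labelled as one.

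*SAP*

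**What the plan says.** Protocol 9.5 names the item among the health-related outcome assessments: "Number of school or working days lost due to the medical condition of the subjects". SAP 8.3.2.18 turns it into a percentage: "The percentage of days lost will be listed by visit for subjects who have more than zero total number of school or work days". The numerator is end date of absence minus start date plus 1, and several absences reported at one visit are summed.

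- **Screening.** The denominator is 3 × 30 + 1. The end is capped at Visit 1, and "if the start date of absence is missing or prior to Visit 1-90, the start date of absence will be set to Visit 1-90".
- **Later visits.** The denominator is current visit date minus previous visit date, plus 1. An absence with no end date, or one that runs past the current visit, is closed on the day of that visit. For a start that is missing or earlier than the day after the previous visit, "the start date of absence will be set to the previous visit date+1".

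The section places these data in a listing for the Randomized Set.

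**The concern.** Within one section, the screening rule and the later-visit rule treat the edge of the window differently. At screening, the days that may be counted and the days in the denominator are the same set. At later visits, the denominator includes the day of the previous visit, which the truncation rule does not allow to be counted. The percentage is therefore on a slightly different scale at screening and afterwards, and the size of the difference depends on how far apart the visits are.

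There is also a labelling problem. The variable is named for school or working days, but numerator and denominator are both spans of calendar dates. The total number of school or work days decides who is listed and does not enter the ratio. A reader of the listing could take the figure as the share of working time lost, which it is not.

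**Working it through.** **Inputs.** The formulas and truncation rules are from SAP 8.3.2.18. Visit spacing is from the schedule of assessments (SAP Table 2–1, Protocol Table 5-1), which collects these data at Visit 1, Visit 2 (Day 1) and Visits 3 to 9. Nominal gaps are 28 days from Visit 1 to Visit 2, 13 days from Visit 2 to 3 (Day 1 to Day 14), 14 days from Visit 3 to 4, 28 days between the visits from 4 to 7, then 21 or 28 days to Visit 8.

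**Screening, the plan's own denominator.** Denominator = 3 × 30 + 1 = 91. Largest countable absence = Visit 1 − (Visit 1 − 90) + 1 = 91. Ratio = 91/91 = 100%. The screening rule is consistent with itself.

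**Later visits.** Let P be the previous visit date, C the current visit date, and D = C − P.

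- Largest single countable absence = C − (P + 1) + 1 = D.
- Stated denominator = C − P + 1 = D + 1.
- Largest ratio = D/(D + 1).

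| D (days) | Single absence over the whole interval, as written | With denominator D |
|---|---|---|
| 13 | 13/14 = 92.9% | 13/13 = 100% |
| 14 | 14/15 = 93.3% | 14/14 = 100% |
| 21 | 21/22 = 95.5% | 21/21 = 100% |
| 28 | 28/29 = 96.6% | 28/28 = 100% |

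The top value can arise without a documented full-interval absence: a record with both dates missing is assigned the whole window by the truncation rules.

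**An ordinary loss.** For N days lost, the shortfall is N/D − N/(D + 1) = N/[D(D + 1)].

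- N = 5, D = 28: 5/29 = 17.2% against 5/28 = 17.9%. Shortfall 5/812 = 0.6 points.
- N = 5, D = 14: 5/15 = 33.3% against 5/14 = 35.7%. Shortfall 5/210 = 2.4 points.

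**Unit.** The numerator is a difference of dates plus 1, and the denominator is 91 or a difference of visit dates plus 1. Both count weekends and other non-working days. The ratio is consistent in its units, but the unit is calendar days.

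**The case against.** The strongest case against raising this is that nothing depends on it. The percentage is listed, not summarized, tested or compared with screening. SAP 3.1 has the listings carry documented data alongside calculated data, so the recorded absence information should be visible next to the percentage. The formula is the same in every arm. Assessing healthcare resource utilization is an "other" objective, and the list of other efficacy variables in Protocol 4.1.3 does not name school or work days lost, although the list is not exhaustive. All of this stands, and it limits the point to a correction of a listing. It does not make the formula right.

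Several stronger readings are tempting and are not supported:

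- *A continuously absent patient would appear to improve after screening.* The listed values could fall from 100% to between 92.9% and 96.6% at the nominal gaps above, but the SAP plans no change from screening for this variable.
- *The later-visit value can never reach 100%.* That holds only when absences do not overlap. Durations are summed and no overlap rule is given, so two records with both dates missing in a 28-day interval would give 56/29 = 193%.
- *The same working loss gives widely different values.* If a Monday-to-Friday pattern is assumed, losing all 20 working days in 28 gives 20/29 = 69.0% when entered as separate weekly absences and 28/29 = 96.6% when entered as one span. This assumes both a work pattern and inconsistent entry. Entry rules sit in the eCRF Completion Guidelines (Protocol 12.3.1), which are not among the documents.
- *The percentage could simply be moved to working days with the data in hand.* The SAP shows a total of school or work days only as a filter, with no reference period, and shows the numerator only as absence dates. Changing the denominator alone would mix units: one continuous 28-day absence over 20 working days gives 28/20 = 140%.

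**Conclusion.** The later-visit rule is wrong as written: its denominator is one day longer than its own counting window. The understatement is a fraction 1/(D + 1) of the correct value, which is 1/15 = 6.7% at 14 days and 1/29 = 3.4% at 28 days. In percentage points, that is at most 6.7 and 3.4 for a single absence filling the interval, and about 0.6 for 5 days lost in 28. This part needs no assumption beyond the SAP text and non-overlapping absences.

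The mismatch affects every visit after screening, including the Baseline Visit (Visit 2), so a reader should not take it as confined to post-Baseline data. It reaches a by-subject listing only. It does not affect the type I error rate, power or any efficacy or safety conclusion. The second part is a matter of labelling: the figure should be presented as calendar days. Whether a working-day percentage would be better, and whether it could be computed, cannot be settled from these documents.

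**What to change.** In SAP 8.3.2.18, set the denominator for visits after screening to current visit date minus previous visit date. Leave the truncation rules and the screening formula as they are. Moving the earliest start back to the previous visit date would also give 100%, but it would count each visit day in two adjoining intervals, so changing the denominator is cleaner.

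State in the SAP and in the listing title or footnote that the percentage is of calendar days.

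The cost is one term in one formula, one label and the matching line of derivation code. The dates needed are already in the formula.

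Use a working-day percentage only if the CRF is confirmed to collect both the working or school days lost and the total working or school days for each visit interval, and then change numerator and denominator together.

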8.3.2.19 Treatment satisfaction

Treatment satisfaction will be collected at visit 7 or at Early Discontinuation Visit. The Treatment Satisfaction Questionnaire for Medication (TSQM)-9 is a 9-item questionnaire developed to provide a suitable measure of treatment satisfaction with medication (Bharmal et al, 2009). It has 5 to 7 Likert response options per item and consists of 3 subscales: effectiveness (3 items), convenience (3 items), and a global satisfaction scale (3 items). The TSQM-9 was

developed from the TSQM 1.42, which has an additional subscale that measures side effects (3 items) (Atkinson et al, 2004). The estimated completion time for this questionnaire is less than 5 minutes. Scores range from 0 (worst) to 100 (best). Treatment satisfaction assessed by TSQM-9 will be listed.

9 PHARMACOKINETICS

9.1 Plasma concentrations of PSL and its major metabolites

Concentrations of PSL and its major metabolites will be determined from blood samples obtained during the Titration and Stabilization and Maintenance Periods (Visits 3, 4, 5, 6 and 7). Individual concentrations of PSL, [REDACTED] metabolite (from venous conventional sampling and dried blood (MITRA) sampling) and [REDACTED] metabolite (from venous conventional sampling) will be listed for subjects in PSL treatment groups for the PK-Set and will include visit, actual daily dose (mg), date and time of the most recent administration, scheduled sampling time per the CRF, actual date and time of sampling, time interval between plasma sample and the most recent administration (in hours with 2 decimal places).

Values below the limit of quantification (LOQ) will be reported as BLQ (below the limit of quantification).

9.2 Plasma concentrations of concomitant AEDs

Blood samples for measurement of concomitant AED concentrations are collected at Visits 1, 2, 6, and 7. The concomitant AED concentrations will be listed by visit and treatment group.

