clinically significant echocardiogram findings (only minor/trace or Grade 1 findings) have been observed. Based on vital signs, ECGs, echocardiograms, and cardiovascular TEAEs evaluated in clinical studies to date, there is no evidence that PSL causes cardiovascular harm in study participants. Data from in vitro studies and clinical pharmacology studies in healthy study participants and epilepsy patients have shown that PSL at high doses moderately increased exposure of sensitive substrates of cytochrome P450 (CYP)2C19. Although less clear, strong inhibitors and inducers of CYP2C19 may also impact the PK and metabolism of PSL and metabolites. Strong inducers of CYP3A4 have also been shown to have a significant interaction with PSL. Therefore, concomitant administration of strong inducers and inhibitors of CYP3A4 with PSL is prohibited. Additionally, when moderate CYP3A4 inhibitors are introduced or withdrawn from a study participant's treatment regimen, the study participant should be closely monitored for changes in clinical response and tolerability. Risks associated with suicidal ideation and behavior, pregnancy and lactation, worsening of seizures, and potential overdose are common to all AEDs.

Risk minimization activities for all relevant risks include study protocol inclusion, exclusion, and withdrawal criteria, and safety monitoring measures as deemed appropriate. The routine core pharmacovigilance activities include: signal detection for any new and existing safety concerns, specific follow-up, and aggregate reporting as well as questionnaires for suicidality, withdrawal symptoms, psychiatric and mental status, and anxiety and depression.

Additional routine risk minimization activities include: ICFs that describe the applicable potential risks and discomforts and risks associated with procedures; inclusion, exclusion, and withdrawal criteria and safety monitoring measures as deemed appropriate in clinical study protocols; ECG monitoring for arrhythmias; and clinical laboratory panels for hepatotoxicity. Study participants will also have routine echocardiograms performed, which provide a grading for valvular findings and/or the presence of any accompanying clinical signs/symptoms.

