### 10.1 Pharmacokinetic variables

The PK variables for PSL and [REDACTED] metabolite are described in detail in Section 4.3. Calculations of PK parameters will be made using population PK modeling. Additionally, plasma concentration data for concomitantly administered AEDs will be evaluated by comparing ratios of steady-state levels vs Baseline levels. For details of PK analyses, refer to Section 13.4.2.

Detailed information on the collection, storage, preparation, and shipping of samples will be presented in a Laboratory Manual.

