### **13.4.2 Pharmacokinetic analyses**

Blood concentrations of PSL will be determined from blood samples obtained in the study, during the Titration and Maintenance Periods in order to investigate the PK of PSL.

The PK variables will be derived from population PK modeling eg, CL/F, AUC(0-τ).

The PK parameters of PSL will be listed and summarized using the following descriptive statistics: number of observations, geometric mean, lower and upper 95% CI, geometric coefficient of variation, arithmetic mean, SD, median, and minimum and maximum values. Graphical outputs over time will be produced on the trough plasma PSL concentrations.

Plasma concentration data for concomitantly administered AEDs will be assessed by evaluating ratios of steady-state levels while on maintenance PSL vs Baseline (pre-PSL) levels.

Comparison of PSL blood levels derived from the MITRA sampler with conventional venous sampling may be made.

An exploratory evaluation of the PSL [REDACTED] metabolite may be undertaken.

Exploratory analyses will not include samples from Chinese subjects.

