2.1.3.2 Pharmacokinetic Objectives

The pharmacokinetic (PK) objectives are to:

- Evaluate the steady-state PK profiles of PSL
- Evaluate the impact of enzyme-inducing concomitant AEDs on PSL exposure
- Evaluate concomitant AED (and/or relevant metabolites) plasma levels

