2.4 Other variables

2.4.1 Pharmacokinetic variables

Blood concentrations of PSL will be determined from samples obtained in the study during the Treatment Period in order to investigate the following variables:

- The population PK profiles of PSL

Blood concentrations of concomitantly administered AEDs will also be evaluated for evidence of drug-drug interaction with PSL at steady state.

Comparison may be made between blood concentration data of PSL and [REDACTED] metabolite derived from the volumetric absorptive microsampling MITRA® technology. Additionally, evaluation of PSL and [REDACTED] metabolite in plasma may be undertaken from trough samples. The collection of plasma samples for this comparison may cease during the course of the study based on periodic review of the data.

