9.3 Other PK analyses/variables

Not applicable.

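### The SAP keeps the objective on concomitant AED plasma levels but plans only a listing, so it gives no estimate of any change in AED exposure on padsevonil

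*SAP*

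**What the plan says.** SAP 2.1.3.2 lists among the PK objectives: "Evaluate concomitant AED (and/or relevant metabolites) plasma levels". SAP 2.4.1 gives the matching variable: "Blood concentrations of concomitantly administered AEDs will also be evaluated for evidence of drug-drug interaction with PSL at steady state".

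The protocol states the method twice. Section 13.4.2 says the AED data will be "assessed by evaluating ratios of steady-state levels while on maintenance PSL vs Baseline (pre-PSL) levels", and Section 10.1 says that "plasma concentration data for concomitantly administered AEDs will be evaluated by comparing ratios of steady-state levels vs Baseline levels".

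The current SAP 9.2 gives the sampling visits (1, 2, 6 and 7) and one output: "The concomitant AED concentrations will be listed by visit and treatment group". SAP 9.3, on other PK analyses, reads in full: "Not applicable".

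**The concern.** A listing contains no ratio, summary statistic or interval, so a retained objective has no analysis that can answer it. The design looks built for the ratio. AED doses are to stay stable through the 16-week Treatment Period (Protocol 5.1). Samples are scheduled twice before PSL and twice on treatment in every arm, and Protocol 10.1.1.2 gives the purpose as evaluating interaction with PSL. Table 5-1 asks for the same timing relative to the AED dose on each occasion, within 1 hour.

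At stake is how the results are read. Every subject takes one to three background AEDs. If PSL changed the level of one of them, part of a dose-related change in seizures or CNS adverse events could come by that route. Protocol 2.4 reports that "PSL at high doses moderately increased exposure of sensitive substrates of cytochrome P450 (CYP)2C19", so the question is not idle. Without an estimate by arm, the study report cannot say from a planned analysis whether AED levels moved.

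**Working it through.** The documents state no figure for the AED ratio analysis, so none can be reproduced. The check is a comparison of texts, followed by an illustration of the precision a restored table would have.

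**Comparison of texts**

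| Item | Protocol | Current SAP |
|---|---|---|
| Objective on AED levels | 3.3.2: present | 2.1.3.2: present |
| Interaction variable | 4.3.1: present | 2.4.1: present |
| Samples at Visits 1, 2, 6, 7 | 10.1.1.2 and Table 5-1: yes | 9.2: yes |
| Analysis | 10.1 and 13.4.2: on-PSL/Baseline ratios | 9.2: listing; 9.3: nothing further |
| Baseline for PK | pre-PSL level (13.4.2) | 3.3.2 refers to Section 9, which defines none |
| Declared as a change from protocol | – | 3.9: no row for Section 9 |

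SAP Section 1 lets the protocol govern unless the SAP specifies otherwise. That does not bring the ratios back, because 9.2 specifies a listing. The mismatch lies within the current text: the objective and variable on one side, the only output on the other.

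**Precision of a restored ratio (illustration)**

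The documents give neither the SD of the within-subject log ratio nor the number of subjects on each AED. I assume an SD of 0.2 to 0.5 and 10 to 30 subjects per arm on a given AED.

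- One arm: 90% CI factor = exp[t(0.95, n-1) × SD/√n]
- PSL arm against placebo, n per arm: factor = exp[t(0.95, 2n-2) × SD × √(2/n)]

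The interval is the estimate divided and multiplied by the factor.

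| n per arm | One arm, SD 0.2 to 0.5 | Against placebo, SD 0.2 to 0.5 |
|---|---|---|
| 10 | 1.12 to 1.34 | 1.17 to 1.47 |
| 20 | 1.08 to 1.21 | 1.11 to 1.31 |
| 30 | 1.06 to 1.17 | 1.09 to 1.24 |

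The least favourable cell, in full: 1.734 × 0.5 × √(2/10) = 0.388. Then exp(0.388) = 1.47 and 1/1.47 = 0.68, which is -32% to +47% around a ratio of 1. That cannot exclude a 25% shift. With SD 0.3 and 20 per arm the factor against placebo is 1.17, and a 25% increase could be excluded if the observed ratio were near 1. The table would therefore be useful for commoner AEDs and weak for rare ones. The comparison with placebo is the one to judge by, since the single-arm interval is narrower but has no control for drift over time.

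**The case against.** The case for leaving the plan alone has several sound parts.

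- **The cut was deliberate and is recorded.** SAP 15.1 sets out the removed analysis and its replacement, under a general rationale of early termination and COVID-19. Other lower-tier outputs became listings too, including PSL concentrations in 9.1. Reducing scope in a terminated trial is defensible. This stands, but the rationale does not withdraw the objective, and 3.9 is the place where a reader looks for departures from the protocol.
- **The prior risk is reduced by design.** The reported interaction concerns sensitive CYP2C19 substrates. Protocol 6.2 (criterion 26) excludes subjects taking them and 7.8.2 prohibits them, with omeprazole the named exception (7.8.1). Carbamazepine, phenytoin, primidone and phenobarbital are also excluded. No passage shows that PSL shifts the level of an AED permitted here. This stands.
- **Interactions are studied elsewhere.** Protocol 2.3 lists UP0013, UP0002 and UP0070. The documents reviewed do not give their AED-level results, so this softens the point without settling it.
- **The data are not lost.** The concentrations are still listed by visit and arm, so ratios could be calculated later. This stands too, although such ratios would not be prespecified.

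A reader might infer that a shift in AED levels would bias the primary and safety analyses in favour of, or against, PSL. The documents do not support that. The objective is the effect of PSL given together with AEDs, compared with placebo, and the randomized contrast estimates the effect of adding PSL whatever the pathway. Nor would a ratio table divide the seizure effect between PSL and altered AED exposure; it would show only whether levels moved.

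**Conclusion.** The point holds as a mismatch between a retained objective and its analysis. The SAP keeps the objective and the interaction variable, drops the ratios that the protocol specifies in two places, does not declare this in 3.9, and leaves a reference in 3.3.2 that leads nowhere. The planned analysis therefore gives no estimate of any change in AED exposure. That rests on the text alone and needs no assumption.

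Its weight is moderate. It concerns a PK objective and bears on the interpretation of mechanism and CNS events; the primary efficacy conclusion and the safety comparison are unaffected. An AED-exposure contribution is a possibility to check, and nothing in the documents demonstrates one. How informative the check would be depends on the assumed SD and on the number of subjects per AED with Visit 6 or 7 samples, which the documents do not give.

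**What to change.** Add one descriptive table to SAP 9.2:

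- For each AED with at least 10 subjects in an arm, the geometric mean ratio of the Visit 6/7 concentration to Baseline, by arm including placebo, with a 90% CI.
- Baseline defined as the mean of Visits 1 and 2, or the single value available. This also repairs the reference in 3.3.2.
- Restriction to subjects whose dose of that AED was unchanged.
- The PSL/placebo ratio of ratios, labelled descriptive.
- A row in 3.9 recording how this differs from Protocol 13.4.2.

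The 10-subject threshold, the 90% level and the Baseline definition come from the superseded text reproduced in SAP 15.1. The rest simplifies the mixed model described there and is not a restoration of it. The protocol itself specifies only the ratios.

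If the table is not wanted, amend 2.1.3.2, 2.4.1, 3.3.2 and 3.9 to state that the objective will not be analysed in this report.

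The cost is a little programming on samples already in the schedule, and wide intervals for less common AEDs.
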